The null hypothesis is rejected at 2.5% significance level if the lower bound of the two-sided 95% confidence interval on the proportion of patients with an atrial sensing amplitude decrease of $\leq 50\%$ and atrial sensing amplitude at 1-month post MRI visit of $\geq 1.5\text{mV}$ is greater than 85%.

4.2.3.4 Proportion of patients with ventricular sensing amplitude decrease of $\leq 50\%$ and a sensing amplitude at 1-month post MRI visit of $\geq 5\text{mV}$

The hypothesis for the ventricular sensing threshold is formally expressed as:

H₀: Proportion of patients with a 'ventricular sensing amplitude decrease of $\leq 50\%$ and ventricular sensing amplitude at 1-month post MRI visit of $>5\text{ mV}' \leq 87\%$

H_a: Proportion of patients with a 'ventricular sensing amplitude decrease of $\leq 50\%$ and atrial sensing amplitude at 1-month post MRI visit of $\geq 5\text{ mV}' >87\%$

The null hypothesis is rejected at 2.5% significance level if the lower bound of the two-sided 95% confidence interval on the proportion of patients with a ‘ventricular sensing amplitude decrease of $\leq 50\%$ and ventricular sensing amplitude at 1-month post MRI visit of $\geq 5\text{mV}$ ’ is greater than 87%.

Sample Size

A success is defined as a patient who experiences a decrease in sensing amplitude not exceeding 50%, and a sensing amplitude not less than 5 mV for ventricular measurements and not less than 1.5mV for atrial measurements at the 1 month post-MRI visit from the pre-MRI testing (at MRI visit).

The % of Success (Post-MRI scan Amplitude – Pre-MRI scan Amplitude) is defined as the number of patients with successes divided by the number of analyzable patients.

In another manufacturer’s study involving MRI conditional pacemaker, proportion of patients with ‘sensing amplitude decrease of $\leq 50\%$ and atrial sensing amplitude at 1-month post MRI visit of $\geq 1.5\text{mV}$ ’ was approximately 93%. In the same study, the proportion of patients with ‘sensing amplitude decrease of $\leq 50\%$ and ventricular sensing amplitude at 1-month post MRI visit of $\geq 5\text{mV}$ ’ was approximately 95%.¹⁹ Therefore, an assumption of 93% for successes in the atrium and 95% successes in the ventricle is assumed

A sample size of 165 patients provides 90% power for the atrial endpoint and 138 patients provides 90% power for the ventricular endpoint at the 2.5% significance level.

Analysis

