The analysis will be conducted on the per-protocol population. The per-protocol population includes patients who meet the following criteria:

- Successfully implanted with the Accent MRI™ system
- Have MRI visit data
- Meet the MRI Conditions of Use
- Received an MRI scan (if in the MRI group)
- Have 1-month post MRI visit data
- Have a pacing threshold difference not exceeding 0.5V between the two-month and three month post-implant (MRI scan pre-check), in cases where the MRI visit takes place approximately 9-12 weeks after an implant or system revision procedure since such short-term variability in pacing

performance can be indicative of an abnormal lead/tissue interface that could confound analyses of MRI related effects.

- Have a pre-MRI/pre-waiting period sensing amplitude greater than or equal to 5.0 mV in the ventricle or greater than or equal to 1.5 mV in the atrium.
- Have an atrial lead to be included in the ‘% success (change in atrial sensing amplitude)’ endpoint analysis and/or a ventricular lead to be included in the ‘% success (change in ventricular sensing amplitude)’ endpoint analysis
- Are not in AF at the time of atrial sensing amplitude measurements
- Have an intrinsic heart rate ≥ 30 beats per minute at the time of ventricular and/or atrial capture threshold measurements

The proportion of patients not experiencing an atrial sensing amplitude decrease of $\leq 50\%$ and atrial sensing amplitude at 1-month post MRI visit of >1.5 mV will be calculated. The associated 2.5% lower confidence bound will also be derived. This lower bound will be compared to the OPC of 85% and the endpoint will be considered successful if the lower bound is greater than 85%.

The proportion of patients not experiencing a ventricular sensing amplitude decrease of $\leq 50\%$ and ventricular sensing amplitude at 1-month post MRI visit of > 5 mV will be calculated. The associated 2.5% lower confidence bound will also be derived. This lower bound will be compared to the OPC of 87% and the endpoint will be considered successful if the lower bound is greater than 87%.

All individual primary efficacy endpoints must be successful (reject the null hypothesis at the $\alpha = 2.5\%$ level) for the efficacy endpoint to be successful.

Additional Analyses

The same additional analyses described above in section 4.2.3.1 and 4.2.3.2 will be completed for this endpoint if required.

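### The Analysis text for the two primary sensing endpoints tests failures against the 85%/87% success targets, and the text leaves open whether an amplitude exactly on the cut-off counts as a success

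*Combined protocol and SAP*

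**What the plan says.** Section 4.2.3 sets two sensing endpoints, atrial (4.2.3.3) and ventricular (4.2.3.4). All primary efficacy endpoints must succeed.

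The Sample Size text defines the outcome, with cut-offs of 1.5 mV (atrium) and 5 mV (ventricle) at the 1-month post-MRI visit: "A success is defined as a patient who experiences a decrease in sensing amplitude not exceeding 50%, and a sensing amplitude not less than" the cut-off. The atrial null is rejected "if the lower bound of the two-sided 95% confidence interval on the proportion of patients with an atrial sensing amplitude decrease of" at most 50% and an amplitude of at least 1.5 mV is above 85%. The ventricular rule has the same form, with 5 mV and 87%.

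The Analysis text says something else:

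- Atrial: "The proportion of patients not experiencing an atrial sensing amplitude decrease of" at most 50% "and atrial sensing amplitude at 1-month post MRI visit of >1.5 mV will be calculated". Its lower bound is compared with the criterion, and "the endpoint will be considered successful if the lower bound is greater than 85" per cent.
- Ventricular: "The proportion of patients not experiencing a ventricular sensing amplitude decrease of" at most 50%, with an amplitude above 5 mV, against 87%.

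The cut-off sign also varies:

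| Sign | Where used |
|---|---|
| Strict (>) | both H0 statements; both Analysis sentences |
| Inclusive (≥) | both titles; both Ha; both rejection rules; the success definition; the comparator rates; the per-protocol baseline criterion |

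The baseline criterion admits a pre-scan "sensing amplitude greater than or equal to 5.0 mV in the ventricle or greater than or equal to 1.5 mV in the atrium". In 4.2.3.4, after "The hypothesis for the ventricular sensing threshold is formally expressed as", the alternative refers to atrial amplitude although the 5 mV limit is the ventricular one.

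**The concern.** There are two separate defects in the decision rule.

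**Direction.** A decrease of at most 50% with an adequate amplitude is the desired result. The proportion of patients not experiencing it is a failure proportion, yet it must exceed 85% or 87%. The Analysis text for the capture thresholds (4.2.3.1 and 4.2.3.2) uses the same phrase correctly, because there it is attached to the adverse event, a threshold increase. The sensing sentences probably copied that construction.

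**Cut-off.** With a strict sign in H0 and an inclusive sign in Ha, the two hypotheses describe different events and can both be true. As an illustration, if 84% of patients were above the cut-off with an acceptable decrease and 2% were exactly on it, H0 (84% ≤ 85%) and Ha (86% > 85%) would both hold. A patient stable at exactly 5.0 mV enters the per-protocol set and then fails under the Analysis sentence without any change.

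Every primary endpoint must pass for overall success, and the secondary endpoints are tested only after that (4.2.4). A few boundary patients on one lead could therefore decide the formal result, and the choice of sign could be made after the data are seen.

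**Working it through.** **Inputs (4.2.3.3 and 4.2.3.4).** Criteria p0 = 0.85 (atrial) and 0.87 (ventricular). Assumed success rates p1 = 0.93 and 0.95. One-sided 2.5%. Stated n = 165 and 138 for 90% power. Section 4.1 caps MRI-phase enrolment at 363. The analysable number is not given, so n = 250 below is an illustrative middle value.

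**1. Reproduce the stated sample sizes.** With the null-variance z-test,

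n = [1.960·√(p0(1−p0)) + 1.282·√(p1(1−p1))]² / (p1−p0)²

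- Atrial: (0.6998 + 0.3270)² / 0.08² = 164.7, so 165.
- Ventricular: (0.6591 + 0.2793)² / 0.08² = 137.6, so 138.

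Both match, which shows that the success proportion was the quantity planned for.

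**2. Pass mark under the rejection rules.** The plan names no interval method. The null-variance z-test and the Clopper-Pearson bound agree at the stated n:

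- Atrial: at most 15 failures in 165, that is at least 150 successes (90.9%). Exact power P(X ≤ 15), X ~ Bin(165, 0.07), is 88.3%.
- Ventricular: at most 10 failures in 138, that is at least 128 successes (92.8%). Exact power P(X ≤ 10), X ~ Bin(138, 0.05), is 91.4%.

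**3. The Analysis sentences as written.** Read as the complement of success, the expected proportion is 1 − 0.93 = 7% (11.6 of 165) and 1 − 0.95 = 5% (6.9 of 138), plus any patients exactly on the cut-off. Read as a decrease above 50% with an amplitude above the cut-off, it is a subset of failures and so no larger than 7% or 5%. At 12/165 and 7/138 the Clopper-Pearson lower bounds are 3.8% and 2.1%, against 85% and 87%. The probability of passing is effectively zero.

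**4. How many boundary patients reverse a pass.** Count = (maximum failures) + 1 − (expected failures, rounded), using the z-test limits:

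| Endpoint | n | Max failures | Expected failures | Patients to reverse |
|---|---|---|---|---|
| Atrial | 165 | 15 | 12 | 4 |
| Atrial | 250 | 26 | 18 | 9 |
| Atrial | 363 | 41 | 25 | 17 |
| Ventricular | 138 | 10 | 7 | 4 |
| Ventricular | 250 | 22 | 13 | 10 |
| Ventricular | 363 | 34 | 18 | 17 |

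Expected failures of 17.5 and 12.5 at n = 250 are rounded up. Clopper-Pearson allows one failure fewer for atrial n = 363 and ventricular n = 250, which lowers those two counts to 16 and 9.

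**5. Power if a share b of patients sits exactly on the cut-off and is counted as failing.** The documents give no such share; 1% and 3% are assumptions. Power = P(X ≤ max failures), X ~ Bin(n, 1 − p1 + b):

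| Endpoint | n | b = 0 | b = 1% | b = 3% |
|---|---|---|---|---|
| Atrial | 165 | 88% | 75% | 41% |
| Atrial | 250 | 98% | 93% | 63% |
| Atrial | 363 | >99% | 99% | 82% |
| Ventricular | 138 | 91% | 79% | 45% |
| Ventricular | 250 | >99% | 97% | 73% |
| Ventricular | 363 | >99% | >99% | 85% |

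**The case against.** The strongest reply is that the plan already contains a complete, correctly directed rule. The Analysis text ends by tying success to rejecting the null, and the only explicit rejection rules for these endpoints run the right way with the inclusive sign. The per-protocol bullets also label the endpoints as percentage success, which the Sample Size text defines as successes over analysable patients. No analyst would test failures against an 85% success target, and the error could not produce a false pass.

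For direction this largely stands: the practical risk is small and the near-zero pass probability should not set the weight of the point. For the cut-off it does not stand, because the null hypotheses to be rejected themselves carry the strict sign.

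Other reservations are fair:

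- **Boundary share.** The 1% and 3% figures are assumed. Sensing is read with an incremental test (4.4.6.7), but no step size is given, so it is unknown whether 1.5 or 5.0 mV is a recordable value. The largest power losses pair a 3% share with the minimum n.
- **Interval method.** A Wald bound would allow 17 failures in 165 and 11 in 138 (power about 96% for both), and 6 and 5 boundary patients (17 + 1 − 12; 11 + 1 − 7) would then reverse a pass, not 4.
- **Cost.** The hypotheses sit in a controlled protocol whose endpoints were negotiated with the regulator, so an edit needs a document revision.

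None of these removes the contradiction.

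**Conclusion.** The concern holds. The pass/fail sentences for two co-primary endpoints are wrong as written. They test a quantity expected to be about 7% and 5% against targets of 85% and 87%, where the rejection rules have 88% and 91% power at the stated n. The intended direction can be recovered from the rest of the section and from the reproduced sample sizes, so that part is a correction of wording.

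The open question is the cut-off sign. Most of the text supports the inclusive reading, but H0 and the Analysis sentences say otherwise and nothing states which governs. At the planned failure rates, four on-cut-off patients reverse a pass at the minimum n and about 17 do so at the 363 cap. These counts rest on the null-variance z-test. The power losses also depend on boundary shares that the documents do not supply. The point should be fixed before the data are analysed; it does not call the design or the sample size into question.

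**What to change.** - In H0, Ha and Analysis for 4.2.3.3 and 4.2.3.4, refer to one event: a decrease of at most 50% and a 1-month post-MRI amplitude of ≥1.5 mV (atrial) or ≥5 mV (ventricular). Compare the lower confidence bound of the proportion of patients **meeting** it with 85% and 87%.
- State that the success definition in the Sample Size text governs wherever wording differs.
- Change the strict sign to ≥ in both H0 statements and both Analysis sentences.
- Replace atrial with ventricular in the ventricular Ha.
- As minor harmonisation, write the capture-threshold Analysis sentence in terms of increases of >0.5 V, to match the endpoint titles in 4.2.3.1 and 4.2.3.2.

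The cost is wording plus the document revision needed to carry it. Sample sizes, visits and data collection do not change.

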4.2.4 Secondary Endpoints

The secondary endpoints will be assessed only if all primary safety and efficacy endpoints were significant. The secondary endpoints will be tested sequentially in the order of: system related complications at 12 months, followed by the atrial capture threshold at the MRI visit, and finally the mean ventricular capture threshold at the MRI visit. At the point where a secondary endpoint fails to achieve significance, all further testing of secondary endpoints will stop.

4.2.4.1 Freedom from system-related complications

The hypothesis is formally expressed as:

H_0 : Freedom from system related complications through the 12 month visit $\leq 80\%$

H_a : Freedom from system related complications through the 12 month visit $> 80\%$

The desired outcome is to reject the null hypotheses. The null hypothesis will be rejected at the 5% significance level if the 95% lower confidence limit for the freedom from system related complications at 12 months is greater than 85%.

Simulation was used to calculate the sample size requirements for testing the Kaplan-Meier estimated survival probability for the freedom-from-complication endpoint. The expected proportion of patients free from system related complications at 12 months is 0.975 (95% CI: 0.924, 0.992) using data from the VICTORY pulse generator IDE study (G050191). For a study size of 800 patients and a Type 1 error rate for the hypothesis test of $\alpha = 0.05$ for a one-sided test, the power is greater than 98%.

Patient Group

All patients that have had an attempted implant or a successful implant of an Accent MRI system will be included in this endpoint.

Patients who are lost to follow-up or withdrawn prior to the 12 month follow-up visit due to a system related complication will be analyzed as having experienced a complication at the date of withdrawal. Patients who withdraw for reasons unrelated to a system related complication will be censored at the date of withdrawal.

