Patients who are lost to follow-up or withdrawn prior to the 2 month follow-up visit due to an RA or RV lead related complication will be analyzed as having experienced a complication at the date the complication occurred. Patients who withdraw for reasons unrelated to an RA or RV lead related complication will be censored at the date of withdrawal.

Analysis

The desired outcome is to reject both null hypotheses for the RA and RV endpoints. The RA and RV hypothesis will be tested separately. The null hypothesis for the RA or RV endpoints will be rejected at the 2.5% significance level if the 95% lower limit of a two-sided confidence interval for the freedom from RA or RV lead-related complications by 2 months is greater than 92%. The confidence

interval will be constructed using the log-log transformation of the event free estimate at 2 months.

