4.2.4.2 Bipolar atrial capture threshold at the MRI visit

The hypothesis is formally expressed as:

H₀: The proportion of patients with atrial capture threshold $\leq 2.0V$ at MRI visit is $\leq 85\%$

H_a: The proportion of patients with atrial capture threshold is $\leq 2.0V$ at MRI visit $> 85\%$

The proportion of patients with atrial capture threshold $\leq 2.0V$ at the MRI visit endpoint will be evaluated using a one-sided z-test, with variance calculated using the OPC of 85% at the $\alpha = 2.5\%$ level. The desired outcome is to reject the null hypothesis.

Patient Group

All patients implanted with the Tendril MRI™ lead with pre-MRI testing atrial capture threshold measurements at the MRI visit.

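### The first gated secondary test (4.2.4.1) runs at one-sided 5%, unlike every other confirmatory test (one-sided 2.5%), and no reason is given; a cheap correction, minor in practical impact

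*Combined protocol and SAP*

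**What the plan says.** Section 4.2.4 opens secondary testing only if all primary safety and efficacy endpoints are significant. It then fixes the order, "The secondary endpoints will be tested sequentially in the order of: system related complications at 12 months", followed by the atrial and then the ventricular capture threshold at the MRI visit. Testing stops at the first failure.

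Section 4.2.4.1 gives the level for the first step twice. The decision rule is "The null hypothesis will be rejected at the 5% significance level if the 95% lower confidence limit for the freedom from system related complications" clears the bar. The sample-size text gives "error rate for the hypothesis test of $\alpha = 0.05$ for a one-sided test, the power is greater than 98"%.

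The other confirmatory tests are at one-sided 2.5%:

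- Lead safety, acute and chronic (4.2.1): "The null hypothesis for the RA or RV endpoints will be rejected at the 2.5% significance level if the 95% lower limit of a two-sided" interval exceeds the criterion.
- MRI safety (4.2.2): one-sided alpha of 0.025.
- Capture and sensing (4.2.3): lower bound of a two-sided 95% interval, 2.5% level.
- Second and third secondaries (4.2.4.2 and 4.2.4.3): for the atrial one, the "endpoint will be evaluated using a one-sided z-test, with variance calculated using the OPC of 85% at the" 2.5% level; the ventricular one matches.

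Section 4.2.4.1 also disagrees with itself on the margin. The null is "H_0 : Freedom from system related complications through the 12 month visit $\leq 80"%, but rejection requires that the lower limit for "freedom from system related complications at 12 months is greater than 85"%.

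**The concern.** An all-primaries gate, a fixed order and a stopping rule have one evident purpose, which is to control the chance of a false claim across several tests. A fixed sequence controls that chance only at the largest level used within it. Here the largest level belongs to the step that opens the secondary sequence, and nothing in 4.2.4 to 4.2.4.3 explains why.

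What is at stake is the 12-month system-safety claim. With the margin settled, that claim would carry about twice the false-positive risk of the other confirmatory claims. A borderline result could pass at 5% and fail at 2.5%, and the same result decides whether the two capture-threshold secondaries are tested at all.

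The wording also invites a slip. A 95% lower limit means a 2.5% test in 4.2.1 and a 5% test in 4.2.4.1, and 4.2.4.1 does not name the interval method. An analyst who reuses the lead-safety code would run a different test from the one written.

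**Working it through.** **Inputs.** From 4.2.4.1: n = 800, one-sided alpha 0.05, null 80%, bar 85%, and an expected rate given as "free from system related complications at 12 months is 0.975 (95% CI: 0.924, 0.992"). From 4.2.2 and 4.2.3: null and expected rates of 0.90/0.97, 0.90/0.98, 0.85/0.93 and 0.87/0.95, with 90% power. Assumptions not in 4.2.4.1: the log-log limit (borrowed from 4.2.1) and no censoring.

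**1. The plan's power figure.** With p0 the null or bar, p1 the true rate and q = 1 − p, power = Φ{[(p1 − p0)√n − z√(p0q0)] / √(p1q1)}.

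- p0 = 0.85, p1 = 0.975, alpha 0.05: (3.5355 − 0.5873)/0.1561 = 18.9.
- Same, alpha 0.025: (3.5355 − 0.6999)/0.1561 = 18.2.
- p0 = 0.85, p1 = 0.924 (lower end of the cited interval): 5.68 at 0.05 and 5.26 at 0.025, so power exceeds 0.9999999 at 0.025.

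Power is higher still against 80%. The stated figure of more than 98% is reproduced and holds at either level.

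**2. The level used elsewhere.** n = {[z(1−alpha)√(p0q0) + z(0.90)√(p1q1)] / (p1 − p0)}². For MRI safety at 0.025 this is [(1.960 × 0.3000 + 1.2816 × 0.1706)/0.07]² = 132.8.

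| Endpoint | Plan | alpha 0.025 | alpha 0.05 |
|---|---|---|---|
| MRI safety | 133 | 133 | 104 |
| Capture | 93 | 93 | 71 |
| Atrial sensing | 165 | 165 | 131 |
| Ventricular sensing | 138 | 138 | 109 |

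Of the two levels, only one-sided 2.5% reproduces the plan's sizes.

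**3. Bound for the sequence.**

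- A primary null is true: the gate opens with probability at most 2.5%.
- All primaries are effective and the first secondary null is true: any false secondary claim requires the first step to pass, so the bound is that step's level, 5%. A simulation with the gate open gave 0.0500.
- The first true null is the second or third secondary: the bound is 2.5%.

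**4. Size of the difference, n = 800.** With S the event-free proportion, the lower limit is S^exp(z·se), where se = √[(1 − S)/(nS)] / |ln S|. At 103 complications, S = 0.87125, se = 0.0986 and the limit at z = 1.645 is 0.8504. At 104 it is 0.8490. At z = 1.960 the limit is 0.8500 (just above 0.85) for 100 complications and 0.8487 for 101. The false-pass rate is the exact binomial probability of a pass with the true rate at the margin.

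| Margin | Level | Most complications that pass | False-pass rate |
|---|---|---|---|
| 85% | 5% | 103 | 4.90% |
| 85% | 2.5% | 100 | 2.47% |
| 80% | 5% | 141 | 4.94% |
| 80% | 2.5% | 137 | 2.18% |

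If losses of 10% or 20% are assumed (effective n of 720 or 640), the rates are 5.0–5.2% at the 5% level and 2.0–2.5% at the 2.5% level.

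**5. The rule as literally written.** With the 85% bar and a true rate of 80%, the chance of at most 103 complications in 800 is 7.6 × 10⁻⁸ (6.5 × 10⁻⁷ for the same rule at n = 640).

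**6. Where the level changes the result.** The two levels disagree only at 101–103 complications (85% margin) or 138–141 (80% margin). The plan expects about 800 × 0.025 = 20, or about 800 × 0.076 = 61 at the lower end of its interval. The chance of landing in 101–103 is 4 × 10⁻⁷ at a true rate of 0.924 and 0.6% at 0.90.

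**The case against.** The 5% level is explicit, stated twice, and internally consistent within 4.2.4.1. It applies to a secondary endpoint that is reached only after nine primaries succeed at 2.5%, so the primary claim is untouched. The convention that gated secondaries share the primary level is not something this plan declares. Each meaning of the 95% limit is also clear where it stands. All of this is fair. It makes the point smaller, but it does not supply the missing reason for a looser level at the step that opens the hierarchy.

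A reader might infer more than the documents support:

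- **That the family-wise rate is 5% as the plan stands.** It is not. Against the written 80% null, the written 85% bar gives an error near zero. The 5% appears only once null and bar are aligned, and then as an upper bound.
- **That this is twice the trial's declared level.** No trial-wide or family-wise level is stated; 2.5% is inferred from the individual tests.
- **That every other test in the trial uses 2.5%.** This is true of the confirmatory tests. The gender comparisons in 4.2.5 use 0.15, outside the sequence.
- **That the capture-threshold claims are inflated too.** Each still has to pass its own 2.5% test.

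The practical objection also stands: at the plan's expected rates both levels give the same result.

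**Conclusion.** The inconsistency is real and unexplained, and its practical impact is minor. Once the 80% and 85% figures are reconciled to either value, the hierarchy's worst-case false-positive rate is up to 5% instead of 2.5%: about 4.9% against 2.2–2.5% at n = 800. That worst case requires every primary to be truly effective and freedom from system complications to lie at the margin, and it concerns the system-complication claim alone. The figures rest on a log-log limit and no censoring; the assumed losses of 10–20% move them little. Correcting the margin alone would leave the looser level in place and make it operative. The extra alpha buys no useful power under the plan's own assumptions, so this is a cheap improvement and not a threat to the trial's main conclusions.

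**What to change.** In the edit that reconciles 80% and 85% in 4.2.4.1:

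- Test at one-sided 2.5%: reject if the lower limit of the two-sided 95% Kaplan-Meier confidence interval, log-log as in 4.2.1, exceeds the chosen margin.
- Restate the sample-size sentence with alpha = 0.025, one-sided. The claim of more than 98% power can stay.

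The whole gated sequence is then bounded at 2.5%. No patients are added. The pass limit becomes 3 complications stricter out of 800 at an 85% margin (103 to 100), or 4 stricter at 80% (141 to 137).

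If the sponsor intends 5%, 4.2.4 should say so, give the reason, and state that the secondary family is controlled only at one-sided 5%. The interval method should be named in either case.

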Patients who are lost to follow-up or withdrawn prior to the 12 month follow-up visit due to an RA or RV lead related complication will be analyzed as having experienced a complication at the date of the complication. Patients who withdraw for reasons unrelated to an RA or RV lead related complication will be censored at the date of withdrawal.

Analysis

The desired outcome is to reject both null hypotheses for the RA and RV endpoints. The RA and RV hypothesis will be tested separately. The null hypothesis for the RA or RV endpoints will be rejected at the 2.5% significance level if the 95% lower limit of a two-sided confidence interval for the freedom from RA or RV lead-related complications between 2 months and 12 months is greater than 95%. The confidence interval will be constructed using the log-log transformation of the event free estimate at 12 months.

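### Section 4.2.4.1 sets an 80% null at the 5% level but rejects only above 85%, and the Analysis text for both primary sensing endpoints computes the wrong proportion

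*Combined protocol and SAP*

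**What the plan says.** **System-related complications (4.2.4.1).** The null is freedom from complications through 12 months of at most 80%, and the alternative is above 80%. The decision rule claims a 5% level and requires that "the 95% lower confidence limit for the freedom from system related complications at 12 months is greater than 85" percent. The sample-size text gives 800 patients, a one-sided alpha of 0.05, an expected rate of 0.975 (95% CI 0.924 to 0.992) and power above 98%. It refers to a Kaplan-Meier estimate but names no method for the confidence limit.

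**Place in the sequence (4.2.4).** "The secondary endpoints will be assessed only if all primary safety and efficacy endpoints were significant". This endpoint is the first of three, and "At the point where a secondary endpoint fails to achieve significance, all further testing of secondary endpoints will stop".

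**Primary sensing endpoints (4.2.3.3 and 4.2.3.4).** Under Sample Size, success is a fall in sensing amplitude of no more than 50% together with a 1-month amplitude of at least 1.5 mV (atrial) or 5 mV (ventricular). The rejection rules require the lower bound on that success proportion to exceed 85% or 87%. The Analysis text that follows instead calculates the proportion of patients not experiencing a decrease of ≤ 50% with an amplitude above 1.5 or 5 mV, and compares that proportion with the same 85% and 87%.

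**The concern.** In 4.2.4.1 the null, the significance level and the rejection limit cannot all describe one test. If 80% is the goal, the limit is 5 points too high. If 85% is the goal, both hypotheses are wrong. The other endpoints that state a confidence-limit rule use the value in their own null: the acute lead rule requires the limit for freedom from "lead-related complications by 2 months is greater than 92" percent, the chronic rule "lead-related complications between 2 months and 12 months is greater than 95" percent, and the capture (90%) and sensing (85%, 87%) rules do the same. Section 4.2.4.1 is the exception, so a deliberate convention of setting stricter limits is unlikely. An unresolved goal invites a choice after the data are seen, and that choice would also decide whether 4.2.4.2 and 4.2.4.3 are tested.

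The sensing sentences state what is to be calculated for two primary endpoints, both of which must succeed. Read literally, they ask for a proportion that should be small and require it to exceed 85% or 87%.

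**Working it through.** **Part (a): 80% or 85%**

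Inputs from 4.2.4.1: n = 800, one-sided alpha 0.05, goals 0.80 and 0.85, expected rate 0.975. Assumed: no censoring, and a log-log limit, because for the chronic lead endpoints the interval is "constructed using the log-log transformation of the event free estimate at 12 months".

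Lower limit: L = p^exp(z·s), with p = r/n, s = √[p(1−p)/n] / (p·|ln p|) and z = 1.645.

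- 80% goal: r = 658 gives L = 0.7990 and r = 659 gives L = 0.8003. Pass at ≥ 659 (82.4%).
- 85% goal: r = 696 gives L = 0.8490 and r = 697 gives L = 0.8504. Pass at ≥ 697 (87.1%).
- Exact one-sided 95% limits give the same 659 and 697. With z = 1.96 the cut-offs are 663 and 700.

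The plan's own figure first: at 0.975 the power is about 1.00 under either goal, so the stated power above 98% is reproduced and does not reveal which goal was used. Binomial probability of passing:

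| True freedom | 80% goal (≥ 659) | 85% goal (≥ 697) |
|---|---|---|
| 0.80 | 0.049 | 0.000000076 |
| 0.85 | 0.98 | 0.049 |
| 0.88 | 1.00 | 0.79 |
| 0.90 | 1.00 | 0.996 |
| 0.924 | 1.00 | 1.00 |
| 0.975 | 1.00 | 1.00 |

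The written rule is therefore a 5% test of a null at 85%. The verdicts differ for 659 to 696 event-free patients (82.4% to 87.0%), that is, 800 − 696 = 104 to 800 − 659 = 141 patients with an event.

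Reachability, given that the four lead-safety tests must pass first (800 RV and 400 RA leads, two-sided 95% log-log limit, no censoring):

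- Most events allowed: RV acute 48, RV chronic 27, RA acute 21, RA chronic 11. The sum is 107 if no patient is counted twice.
- Expected at the plan's conservative rates (0.97 acute, 0.98 chronic): 800×0.03 + 800×0.02 + 400×0.03 + 400×0.02 = 24 + 16 + 12 + 8 = 60. Reaching 104 would take 44 more patients with non-lead complications.
- Expected at the registry rates in 4.2.1 (RV 0.993 and 0.998; RA 0.995 and 0.996): 5.6 + 1.6 + 2.0 + 1.6 = 10.8, so about 93 more would be needed.

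These counts assume that system-related complications include lead-related ones.

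**Part (b): sensing endpoints**

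Reproduce the plan's sample sizes, taking success as the quantity tested: n = [(1.960·√(p0(1−p0)) + 1.282·√(p1(1−p1))) / (p1−p0)]².

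- Atrial, 0.85 against 0.93: [(0.6998 + 0.3270)/0.08]² = 164.7, so 165, as stated.
- Ventricular, 0.87 against 0.95: [(0.6591 + 0.2793)/0.08]² = 137.6, so 138, as stated.

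The planning is for the success proportion. Read literally, the Analysis text would compare about 1 − 0.93 = 7% with 85%, and 1 − 0.95 = 5% with 87%. With an exact 2.5% lower bound, a pass would need at least 150 of 165 and 128 of 138 patients to miss the success condition, which is effectively impossible at the assumed rates. If the negation covers only the decrease, the sentence describes patients whose amplitude fell by more than 50% but stayed adequate. That is not success either.

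**Editorial slips in the same text, with no power consequence**

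- The sensing nulls and Analysis sentences use > where the success definition implies ≥ at 1.5 and 5 mV. On this account the literal reading is the complement of success only up to the boundary value.
- The ventricular alternative hypothesis says atrial.
- The capture Analysis sentence (4.2.3.1/4.2.3.2) gives 0.5 V without an inequality, although the rule (post ≤ pre + 0.5 V) stands under Sample Size there.

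**The case against.** The strongest reply is that neither defect is likely to change a result. The 85% rule is conservative and cannot inflate type I error. Conflicting verdicts need at least 104 patients with events when 800 × 0.025 = 20 are expected; the chance of 104 or more is about 5×10⁻⁴² at 0.975 and 8×10⁻⁸ at 0.924, the lower end of the plan's own interval. If RA leads come only at the anticipated minimum of 30% (240 leads, section 4.1), the RA allowances fall to 10 and 5 events and the lead total to 48 + 27 + 10 + 5 = 90, so lead events alone could not reach 104. The interval method matters little, since log-log and exact limits agree. For sensing, the titles, alternatives, rejection rules, success definition and sample sizes all point one way, so no competent analyst would program the literal sentence. Some of the single-symbol slips could also come from reading the PDF.

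All of this stands as to weight. It does not remove the defects. Nothing in the plan says whether 80% or 85% is the goal, and that goal is what will be reported and judged. The sensing sentences are wrong on either reading, and they are the instruction an analyst would implement.

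**Conclusion.** Both points hold and should be fixed.

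(a) Section 4.2.4.1 gives two performance goals, with cut-offs 38 patients apart (659 and 697 of 800). The actual type I error at the stated null is about 0.00000008 against a claimed 0.05. The direction is conservative and power is unaffected at the expected rate. The case for acting is an undefined success criterion at the head of a fixed sequence, not a realistic threat to the outcome. The figures rest on complete follow-up of 800 patients and a one-sided 95% log-log or exact limit; with z = 1.96 the gap remains (663 and 700).

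(b) The sensing Analysis text names the wrong proportion for two primary endpoints. The intended one is certain from the rest of 4.2.3.3 and 4.2.3.4, so this is a drafting correction with only one possible answer.

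**What to change.** Before any data are analysed:

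- **4.2.4.1:** the sponsor states one goal, 80% or 85%, whichever was agreed, in the null, the alternative and the rejection rule, and names the interval method and its sidedness.
- **4.2.3.3 and 4.2.3.4, Analysis:** define the proportion as patients with a sensing decrease ≤ 50% and a 1-month amplitude ≥ 1.5 mV (atrial) or ≥ 5 mV (ventricular).
- **Sensing hypotheses:** use ≥ in both nulls, and change atrial to ventricular in the ventricular alternative.
- **4.2.3.1/4.2.3.2, Analysis:** state an increase ≤ 0.5 V.

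The cost is wording in the protocol/SAP. Sample size, visits and data collection do not change.
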